# 6.1.6 AEs of Special Interest

Hy's Law:

- Potential Hy's Law, defined as ALT or AST  $\geq$ 3×ULN with coexisting total bilirubin  $\geq$ 2×ULN in the absence of ALP  $\geq 2 \times ULN$ , with no alternative explanation for the biochemical abnormality (ie, without waiting for any additional etiologic investigations to have been concluded). Followoilation up information should be reported if an alternative etiology is identified during investigation and monitoring of the study participant.

The detailed information of analysis for Hy's law can be found in 5.6.3.1.1

#### Potentially Clinically Significant Criteria for Safety Endpoints 6.1.7

#### 6.1.7.1 Markedly abnormality criteria for laboratory data

Markedly abnormal values are defined as those with a severity of Grade 3 and above based on the common terminology criteria for adverse events (CTCAE) criteria (U.S. Department of Health and Human Services 2017). Definitions of markedly abnormal values using the Grade 3 cut points are given in the tables below for age ranges of  $\geq 17$  years (Table 10 for markedly abnormal hematology values, Table 11 for markedly abnormal biochemistry values, and Table 12 for markedly abnormal liver function test values). Tables summarizing markedly abnormal values should include a summary (counts and percentages) of markedly abnormal labs observed at any time while on treatment (i.e., treatment-emergent markedly abnormal [TEMA]). For this summary, Baseline values are not considered. The laboratory results classified as Grade 3 or Grade 4 will be summarized and listed separately.

Parameter	Co	nventional	s s	Abnormal	
name	Unit	Criteria	Unit	Criteria	Designation
Hemoglobin	/ 17	<8.0+	/ T	<8.0	AL
	g/dL	>4.0 above ULN	g/L	>4.0 above ULN	AH
Lymphocytes		<0.5	109/J	<0.5	AL
Absolute	10 ⁻⁷ L	>20.0	10 ² /L	>20.0	AH
Neutrophils Absolute	10 ⁹ /L	<1.0	10 ⁹ /L	<1.0	AL
Platelets	10 ⁹ /L	<50	10 ⁹ /L	<50	AL
WBC/Leukocytes	10 ⁹ /L	<2.0	10 ⁹ /L	<2.0	AL
y		>100		>100	AH

normal Hematology Values
n

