 - $\geq 3 \times \text{ULN}$ of any of the following: ALT, AST, alkaline phosphatase (ALP); or $> \text{ULN}$ total bilirubin ($\geq 1.5 \times \text{ULN}$ total bilirubin if known Gilbert's syndrome)
 - White blood cell (WBC) count $< 3.00 \times 10^3 / \mu\text{L}$
 - Absolute neutrophil count $< 1.5 \times 10^3 / \mu\text{L}$
 - Lymphocyte count $< 500 \text{ cells} / \mu\text{L}$
 - Hemoglobin $< 8.5 \text{ g} / \text{dL}$

Any other laboratory abnormality, which, in the opinion of the Investigator, will prevent the study participant from completing the study or will interfere with the interpretation of the study results.

Individual screening tests for which the results are in error, borderline, or indeterminate for inclusion in the study can be repeated once for confirmation during the Screening Period. Upon retesting, study participants whose results remain outside this threshold should not be randomized.

Other exclusions

25. Study participant is a member of Investigator site personnel directly affiliated with this study and/or their immediate families. Immediate family is defined as a spouse, parent, child, or sibling, whether biological or legally adopted.
26. Study participant is a UCB employee or an employee of third-party organizations involved in the study.

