# 5.6.3 Additional Safety Assessments

# 5.6.3.1 Clinical laboratory evaluations

Laboratory values, including markedly abnormal laboratory values will be presented descriptively by treatment group for SS. Tables of markedly abnormal laboratory values (see section 6.1.7.1) and those based on CTCAE grade (see section 6.1.8) will only include selected variables.

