# 5.6.3.1.1 Laboratory values over time

For tables where data are summarized by visit, unscheduled and repeat visits will not be summarized, but these data will be included in listings. For tables where multiple measurements over a period of time are considered (as in shift tables), unscheduled and repeat visits will be considered as long as they were collected in the period being summarized. All summaries will be presented in International System of Units and will be based on observed case values. In the case where laboratory values are below the LLQ, then these will be set to the midpoint between 0 and the lower limit of quantification for the purpose of summarizing the data.

The following summaries will be presented for data collected during the Treatment Period, SFU data will be included in listings only (unless otherwise specified).

- A summary of the absolute and change from Baseline values in each laboratory variable by treatment group and visit.
- A summary of the number and percentage of study participants experiencing markedly abnormal values at any time while on treatment (assessment on or following the first dose

of study treatment through to the end of the time at risk (see section 5.6.1)) by laboratory variable and treatment group

- A summary of the number and percentage of study participants with a given CTCAE grade (0,1,2,3, or 4) based on minimum/maximum post-baseline value by laboratory variable and treatment group
- A shift table of the number and percentage of study participants experiencing CTCAE grade 0,1,2,3, or 4 values (as applicable) at Baseline to maximum post-Baseline CTCAE grade, by laboratory variable and treatment group
- A figure presenting neutrophil CTCAE grade over time for study participants with at least one markedly abnormal neutrophil value (Grade 3 or above).
- Spaghetti plots presenting ALT values over time for study participants with at least one markedly abnormal ALT value (Grade 3 or above) (Including SFU).
- Spaghetti plots presenting AST values over time for study participants with at least one markedly abnormal AST value (Grade 3 or above) (Including SFU).
- A by-study participant listing of all laboratory data (including urinalysis) will be provided. This listing will be presented by treatment group and will include: center, subject identifier, age, sex, race, weight, visit, laboratory variable, result (with abnormal values flagged as "L" or "H" accordingly) and unit.

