#### Definition of CTCAE grades 6.1.8

# Table 14: Definitions of CTCAE grades by biochemistry parameter

Parameter (unit)	Definition	Unit	Grade 1	Grade 2	Grade 3	Grade 4
Creatinine	High	umol/L	>ULN-1.5 x ULN	(>1.5-3.0) x ULN	(>3.0-6.0) x ULN	6.0 x ULN
Sodium	Low	mmol/L	130- <lln< td="">N/A	120-<130	<120	</lln<>	N/A	120-<130	<120
Sodium	High	mmol/L	>ULN-150	>150-155	>155-160	>160
Potassium	Low	mmol/L	3.0- <lln< td="">3.0-<lln< td="">2.5<3.0	<2.5	</lln<>	</lln<>	3.0- <lln< td="">2.5<3.0	<2.5	</lln<>	2.5<3.0	<2.5
Potassium	High	mmol/L	>ULN-5.5	>5.5-6.0	>6.0-7.0	>7.0
Calcium	CLow	mmol/L	2.0- <lln< td="">1.75-<2.0	1.5-<1.75	<1.5	</lln<>	1.75-<2.0	1.5-<1.75	<1.5
Calcium	High	mmol/L	>ULN-2.9	>2.9-3.1	>3.1-3.4	>3.4
Magnesium	Low	mmol/L	0.5- <lln< td="">0.4-<0.5	0.3-<0.4	< 0.3	</lln<>	0.4-<0.5	0.3-<0.4	< 0.3
Magnesium	High	mmol/L	>ULN-1.23	N/A	>1.23-3.30	>3.30
Cholesterol	High	mmol/L	>ULN-7.75	>7.75- 10.34	>10.34- 12.92	>12.92

Triglycerides	High	mmol/L	1.71-3.42	>3.42-5.7	>5.7-11.4	>11.4
	_					

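### SAP Table 10 prints the same hemoglobin limits under g/dL and g/L, so the g/L limits are ten-fold too low and conflict with Table 15; the two low-glucose limits in Table 11 also disagree.

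*SAP*

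**What the plan says.** SAP 6.1.7.1 sets the rule: "Markedly abnormal values are defined as those with a severity of Grade 3 and above" of the CTCAE. It then says where the limits are: "Definitions of markedly abnormal values using the Grade 3 cut points are given in the tables below".

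- **Table 10, hemoglobin.** The conventional column (g/dL) gives <8.0 as abnormal low and ">4.0 above ULN" as abnormal high. The standard column (g/L) gives the same two entries.
- **Table 15, hemoglobin (section 6.1.8).** Grade 3, in g/L, is <80 on the low side and >40 above BL on the high side.
- **Table 11, glucose.** Low is <40 mg/dL and <1.7 mmol/L. High is >250 mg/dL and >13.9 mmol/L.
- **Table 14** ("Definitions of CTCAE grades by biochemistry parameter") has no glucose row.

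SAP 5.6.3.1 refers the markedly abnormal tables to section 6.1.7.1. SAP 5.6.3.1.1 says of the laboratory output: "All summaries will be presented in International System of Units". The same section plans a separate summary of "study participants with a given CTCAE grade" and a grade shift table, for which 5.6.3.1 points to section 6.1.8. Protocol 9.4.1.3 leaves the definition of markedly abnormal to the SAP.

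**The concern.** One quantity cannot have the same numerical limit in two units that differ by a factor of ten. The affected column is the one that matches the SI units announced for the laboratory summaries, so a programmer following the SAP literally would use it.

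The table of treatment-emergent markedly abnormal values would then be wrong in both directions for hemoglobin. No plausible value is low enough to be flagged, while values only slightly above ULN are counted as markedly high. The same report would carry CTCAE-grade and shift tables built on Table 15, so a hemoglobin of 78 g/L would be Grade 3 there and not markedly abnormal here, although the SAP equates the two.

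Two smaller conflicts sit beside this. Tables 10 and 15 measure high hemoglobin from different reference points. The low-glucose pair in Table 11 does not convert, and no glucose row exists among the CTCAE grades to expose the error.

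**Working it through.** **Hemoglobin scale.** Inputs: the Table 10 g/dL column and the Table 15 Grade 3 cells in g/L.

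- Low: 8.0 g/dL × 10 = 80 g/L. Table 15 prints 80; Table 10 prints 8.0.
- High: 4.0 g/dL × 10 = 40 g/L. Table 15 prints 40; Table 10 prints 4.0.
- Literal reading of the printed g/L cells: 8.0 g/L ÷ 10 = 0.8 g/dL, and 4.0 g/L ÷ 10 = 0.4 g/dL.

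The g/dL column therefore reproduces the Table 15 magnitudes exactly, and both g/L cells are low by a factor of 10. Hemoglobin is the only Table 10 row whose unit changes between columns; the other rows are in 10⁹/L on both sides, so repeating the number there is correct.

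**What the low limit would require.** Protocol 5.2, criterion 24, excludes hemoglobin below 8.5 g/dL at Screening, that is 85 g/L. A participant at that limit would have to fall by more than 85 − 8 = 77 g/L, or 77/85 = 90.6%, to be flagged.

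**High-hemoglobin reference.** Reading BL as baseline, the corrected Table 10 rule would be value > ULN + 40 g/L, while Table 15 has value > baseline + 40 g/L. The thresholds differ by ULN − baseline for each participant, so the unit correction alone does not align the two tables.

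**Glucose.** The conversion factor comes from Table 11's own high pair.

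- Factor: 250/13.9 = 17.99 mg/dL per mmol/L. With 13.9 anywhere from 13.85 to 13.95, it is 17.92 to 18.05.
- 40 mg/dL: 40/17.99 = 2.22 mmol/L (2.22 to 2.23). Printed: 1.7.
- 1.7 mmol/L: 1.7 × 17.99 = 30.6 mg/dL. Allowing for rounding of both figures: 1.65 × 17.92 = 29.6 to 1.75 × 18.05 = 31.6. Printed: 40.
- Gap: 2.22 − 1.7 = 0.52 mmol/L, or 40 − 30.6 = 9.4 mg/dL, which rounding does not cover.

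**Control on the rest of Table 11.** The other parameters with two converted pairs agree within rounding.

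| Parameter | Pairs | Result |
|---|---|---|
| Calcium | 7.0/1.75 and 12.5/3.1 | 4.00 and 4.03 |
| Magnesium | 3.0/1.23 = 2.44; 0.9/2.44 | 0.37, printed 0.4 |

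Cholesterol and triglycerides have one pair each and cannot be checked this way. Low glucose is the only pair found not to convert.

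**The case against.** The best reply is that the rule itself is right. Section 6.1.7.1 says Grade 3, Table 15 prints the correct low limit in g/L, and 8.0 g/L is so implausible that a programmer would probably notice. The SI sentence governs how results are presented and does not state which column the flags come from; flags could be derived in g/dL and displayed in SI. The standard column is not consistently SI either, since Table 12 lists total bilirubin in mg/dL under both headings. The markedly abnormal tables are limited to selected variables that 5.6.3.1 does not name. Low hemoglobin would still appear in the grade and shift tables and in the listing. The glucose point rests on one cell of a table that was damaged in text extraction.

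Much of this limits the harm, and two points are accepted in full: the effect depends on programming from the g/L column, and the glucose cells should be checked against the original SAP before any change. It does not remove the error. A programmer who silently corrected hemoglobin would be departing from a prespecified definition. The ULN or BL conflict and the glucose pair offer no obvious answer to infer. An extraction fault is unlikely for hemoglobin, because both g/L cells repeat the neighbouring g/dL number and the unit label is legible.

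**Conclusion.** The concern holds. Both g/L hemoglobin limits in Table 10 are one-tenth of what its own g/dL column and Table 15 require: 8 against 80 g/L, and 4 against 40 g/L. The high-hemoglobin reference also differs between the two tables, and the low-glucose cells differ by about 0.5 mmol/L (9 mg/dL).

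Confidence is high for hemoglobin. For glucose the mismatch is clear as printed, but the documents do not show which cell is intended. The effect on results assumes that hemoglobin and glucose are among the selected variables and that flags are derived from the SI column. It is confined to the incidence of markedly abnormal laboratory values, a tertiary, descriptive safety endpoint. The co-primary and secondary endpoints and the sample size are untouched. It should be fixed, because two outputs of one report would otherwise contradict each other.

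**What to change.** 1. In Table 10, change the g/L hemoglobin limits to <80 and >40.
2. Choose one reference, ULN or baseline, for high hemoglobin and use it in both Table 10 and Table 15.
3. Check the low-glucose cells in the original Table 11, then reconcile them with each other and with the Grade 3 definition in the CTCAE version that the SAP cites (5.0).
4. Derive the markedly abnormal flags from the corrected tables, and state in 5.6.3.1 which unit column is used and which variables are selected.

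The cost is a few table cells, one reference word and a clarifying sentence before programming. Data collection and participants are not affected.

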# Table 11: Definition of Markedly Abnormal Biochemistry Values

Conventional Standard	
-----------------------	--

Parameter Name	Unit	Criteria	Unit	Criteria	Abnormal Designation	
Creatine	mg/dL	>3.0 x ULN	umol/L	>3.0 x ULN	АН	~
Glucose	/ 17	<40	mmol/L	<1.7	AL	Ŷ.
	mg/dL	>250		>13.9	АН	
Calcium		<7.0	mmol/L	<1.75	AL	
	mg/dL	>12.5		>3.1	AH	
Magnesium		<0.9	mmol/L	<0.4	AL	
	mg/dL	>3.0		@1.23	АН	
Potassium	mmol/L	<3.0	mmol/L	<3.0	AL	
		>6.0		>6.0	АН	
Sodium	mmol/L	<130	mmol/L	<130	AL	
		>155 5	ions	>155	АН	
Cholesterol	mg/dL	>400	mmol/L	>10.34	AH	
Triglycerides	mg/dL	\$ >500	mmol/L	>5.7	AH	

# Table 12 Definition of Markedly Abnormal Liver Function Test Values

	Parameter	Conventional		St	Abnormal	
	Name	Unit	Criteria	Unit	Criteria	Designation
	Alkaline Phosphate	U/L	>5.0 x ULN	U/L	>5.0 x ULN	АН
	ALT	U/L	>5.0 x ULN	U/L	>5.0 x ULN	АН
	AST	U/L	>5.0 x ULN	U/L	>5.0 x ULN	АН
MIS	Total Bilirubin	mg/dL	>3.0 x ULN	mg/dL	>3.0 x ULN	АН
	GGT	U/L	>5.0 x ULN	U/L	>5.0 x ULN	AH

Abbreviations: AH=abnormal high; AL=abnormal low; ALT= alanine aminotransferase; AST = aspartate aminotransferase; dL = deciliter; GGT: gamma-glutamyltransferase; L = liter; mg = milligram; mmol = millimoles;  $\mu$ g = microgram; ULN = upper limit of normal.

#### 6.1.7.2 Markedly abnormality criteria for vital signs

# Table 13: Definitions of Markedly Abnormal Blood Pressure Values

6.1.7.2 Markedly abno	ormality criteria for vital sig	ıs				
The definitions of markedly abr	ormal vital sign values are provi	ded below:				
Table 13: Definitions of Markedly Abnormal Blood Pressure Values						
Parameter (unit)	Markedly Abnormal Low	Markedly Abnormal High				
Systolic blood pressure (mmHg)	<90 and a decrease from	>180 and an increase from				
	Baseline of ≥20	Baseline of ≥20				
Diastolic blood pressure (mmHg)	<50 and a decrease from	>105 and an increase from				
	Baseline of ≥15	Baseline of ≥15				

#### Definition of CTCAE grades 6.1.8

# Table 14: Definitions of CTCAE grades by biochemistry parameter

Parameter (unit)	Definition	Unit	Grade 1	Grade 2	Grade 3	Grade 4
Creatinine	High	umol/L	>ULN-1.5 x ULN	(>1.5-3.0) x ULN	(>3.0-6.0) x ULN	6.0 x ULN
Sodium	Low	mmol/L	130- <lln< td="">N/A	120-<130	<120	</lln<>	N/A	120-<130	<120
Sodium	High	mmol/L	>ULN-150	>150-155	>155-160	>160
Potassium	Low	mmol/L	3.0- <lln< td="">3.0-<lln< td="">2.5<3.0	<2.5	</lln<>	</lln<>	3.0- <lln< td="">2.5<3.0	<2.5	</lln<>	2.5<3.0	<2.5
Potassium	High	mmol/L	>ULN-5.5	>5.5-6.0	>6.0-7.0	>7.0
Calcium	CLow	mmol/L	2.0- <lln< td="">1.75-<2.0	1.5-<1.75	<1.5	</lln<>	1.75-<2.0	1.5-<1.75	<1.5
Calcium	High	mmol/L	>ULN-2.9	>2.9-3.1	>3.1-3.4	>3.4
Magnesium	Low	mmol/L	0.5- <lln< td="">0.4-<0.5	0.3-<0.4	< 0.3	</lln<>	0.4-<0.5	0.3-<0.4	< 0.3
Magnesium	High	mmol/L	>ULN-1.23	N/A	>1.23-3.30	>3.30
Cholesterol	High	mmol/L	>ULN-7.75	>7.75- 10.34	>10.34- 12.92	>12.92

Triglycerides	High	mmol/L	1.71-3.42	>3.42-5.7	>5.7-11.4	>11.4
	_					

# Table 15: Definitions of CTCAE grades by hematology parameter

Parameter (unit)	Definition	Unit	Grade 1	Grade 2	Grade 3	Grade 4
Hemoglobin	Low	g/L	100- <lln< td="">80-<100	<80	N/A	</lln<>	80-<100	<80	N/A
Hemoglobin	High	g/L	>0-20 above BL	>20-40 above BL	>40 above BL	N/A
Platelets	Low	10 ⁹ /L	75- <lln< td="">50-<75	25-<50	<25	</lln<>	50-<75	25-<50	<25
WBC	Low	10 ⁹ /L	3- <lln< td="">2-<3	1-52	<1	</lln<>	2-<3	1-52	<1
WBC	High	10 ⁹ /L	N/A	N/A	⊘100	N/A
Lymphocytes	Low	10 ⁹ /L	0.8- <lln< td="">0.5-<0.8	0.2-<0.5	<0.2	</lln<>	0.5-<0.8	0.2-<0.5	<0.2
Lymphocytes	High	10 ⁹ /L	N/A	>4-20	>20	N/A
Neutrophils	Low	10 ⁹ /L	1.5- <lln< td="">S1.0-<1.5	0.5-<1.0	<0.5	</lln<>	S 1.0-<1.5	0.5-<1.0	<0.5

Note that study participants who meet the decreased potassium criterion of 3.0< LLN, which is specified as the decreased potassium lab criterion for both CTCAE Grade 1 and Grade 2, will be counted as Grade 2.

# 6.1.9 MedDRA algorithmic approach to anaphylaxis

The SMQ *Anaphylactic reaction* consists of three parts (select the terms according to the applicable MedDRA version):

• A **narrow search** containing PTs that represent core anaphylactic reaction terms (Category A – core anaphylactic reaction terms)

For MedDRA v19.0:
Anaphylactic reaction
Anaphylactic shock
Anaphylactic transfusion
reaction
Anaphylactoid reaction
Anaphylactoid shock
Circulatory collapse
Dialysis membrane reaction
Kounis syndrome
Shock

Shock symptom Type I hypersensitivity

- A broad search that contains additional terms that are added to those included in the narrow ٠

A broad	search that contains additional term	is that are added to those included in the narrow
search. T	These additional terms are signs and s	symptoms possibly indicative of anaphylactic
reaction	and categorized in B, C or D	:1.0

 
Cate
 
	gory B (Upper Airway/Respirator	y Terms)
	For ModDPA v19 0.	
	A gute respiratory foilure	Nasal obstruction
	Acute respiratory failure	Asar obstruction
	Astnma	Oedema mouth
	Bronchial oedema	Oropharyngeal spasm
	Bronchospasm	Oropharyngeal swelling
	Cardio-respiratory distress	Respiratory arrest
	Chest discomfort	Respiratory distress
	Choking	Respiratory failure
	Choking sensation	Reversible airways obstruction
	Circumoral oedema	Sensation of foreign body
	Cough	Sneezing
	Cyanosis	Stridor
	Dyspnoea	Swollen tongue
	Hyperventilation	Tachypnoea
	Irregular breathing	Throat tightness
	Laryngeal dyspnoea	Tongue oedema
	Laryngeal oedema	Tracheal obstruction
	Laryngospasm	Tracheal oedema
	Laryngotracheal oedema	Upper airway obstruction
	Mouthswelling	Wheezing

# Category C (Angioedema/Urticaria/Pruritus/Flush terms)

For MedDRA v19.0:	
Allergic oedema	Oedema
Angioedema	Periorbital oedema
Erythema	Pruritus
Eye oedema	Pruritus allergic
Eye pruritus	Pruritus generalised
Eye swelling	Rash
Eyelid oedema	Rash erythematous
Face oedema	Rash generalised

UCB Statistical Analysis Plan

Flushing	Rash pruritic
Generalised erythema	Skin swelling
Injection site urticaria	Swelling
Lip oedema	Swelling face
Lip swelling	Urticaria
Nodular rash	Urticaria papular
Ocular hyperaemia	

**Category D (Cardiovascular/Hypotension terms)** 

scular/Hypotension terms)
For MedDRA v19.0:
Blood pressure decreased
Blood pressure diastolic
decreased
Blood pressure systolic
decreased
Cardiac arrest
Cardio-respiratory arrest
Cardiovascular insufficiency
Diastolic hypotension
Hypotension

- An algorithmic approach which combines a number of anaphylactic reaction symptoms in order to • increase specificity. A case must include one of the following where both occur on either the same day as when an injection was administered or one day after, and for scenarios where two events must have been reported, both events must have occurred within one day of each other (as anaphylaxis is an acute event, imputed dates should not be used in the algorithmic approach):
  - A narrow term or a term from Category A; 0
  - A term from Category B (Upper Airway/Respiratory) AND a term from Category C -0 (Angioedema/Urticaria/Pruritus/Flush);
  - A term from Category D (Cardiovascular/Hypotension) AND [a term from Category B (Upper 0 Airway/Respiratory) OR a term from Category C - (Angioedema/Urticaria/ Pruritus/Flush)]

#### Treatment Compliance 6.1.10

Study treatment compliance will be calculated and summarized for the SS.

Treatment compliance will be calculated as:

(Actual number of completed injections/Expected number of injections)  $\times$  100

In this study, Baseline visit and Weeks 4, 8, 12 are dosing visits. For study participants who complete all injections as planned, the expected number of injections is 8. For participants who permanently discontinue treatment, the number of expected injections is based on the time of early discontinuation relative to the dosing visits.

Bimekizumab

Compliance will be summarized descriptively by treatment group and overall. The number and percentage of study participants meeting certain compliance thresholds (<75% and  $\geq 75\%$ ) will also be reported.

#### **Appendix 2 Changes to Protocol-Planned Analyses** 6.2

Zation According to the protocol, for the secondary efficacy endpoint of percentage change from Baseline in BSA affected by PSO Week 16, the outcomes for study participants with an intercurrent event, which is defined as discontinuation of IMP prior to Week 16, will be imputed using multiple imputation (MI). Due to the small sample size of this study, MI approach may not be valid and will be changed using LOCF instead. In addition, missing data not associated with discontinuation of IMP will also be imputed using LOCF. The same update will be applied to PHO-9, of which the missing data will be imputed using LOCF instead of MI approach.

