To assess the effect of bimekizumab on depression occurrence or worsening	
 • Change from Baseline in PHQ-9 at Week 16
Tertiary	
To evaluate the PK of bimekizumab in study participants with moderate to severe PSO	
 • Plasma bimekizumab concentrations over the study duration
To evaluate the immunogenicity of bimekizumab	
 • Anti-bimekizumab antibody status over the study duration
To assess the efficacy of bimekizumab compared with placebo over time	
 • PASI75 response over time • PASI90 response over time • PASI100 response over time • Absolute and percent change from Baseline in PASI score over time • Percentage of study participants with absolute PASI score ≤ 1, ≤ 2, ≤ 3, and ≤ 5 over time • Time to PASI50, PASI75, PASI90, and PASI100 response • IGA 0/1 response (with at least 2-category improvement from Baseline) over time • IGA 0 response (with at least 2-category improvement from Baseline) over time • Scalp-specific IGA (scalp IGA) 0/1 response (clear or almost clear with at least 2-category improvement from Baseline for participants with scalp PSO at Baseline) over time • Percentage of study participants with absolute BSA affected by PSO=0%, $\leq 1\%$, $\leq 3\%$ and $\leq 5\%$ over time • Percentage of study participants achieving a DLQI Total Score of 0 or 1 over time • Change from Baseline in DLQI Total Score over time • PSD (P-SIM) response rates over time • Change from Baseline in PSD (P-SIM) scores over time
To further evaluate the safety of bimekizumab compared with placebo over time	
 • Selected safety topics of interest TEAEs • Change from Baseline in laboratory variables (hematology and biochemistry) • Incidence of markedly abnormal laboratory values • Change from Baseline in vital signs • Incidence of markedly abnormal vital signs

Objectives	Endpoints
	
 • Change from Baseline in ECG parameters • ECG outliers • Change from Baseline in PHQ-9 • Incidence of PHQ-9 scores ≥ 15 and ≥ 20 • Incidence of suicidal ideation, suicidal behavior, or self-injurious behavior without suicidal intent (from C-SSRS)

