3. Intercurrent event handling: A hypothetical strategy will be implemented in which the estimand targets the treatment difference in a scenario where an intercurrent event does not occur, such that outcomes for study participants without an intercurrent event are as observed, and outcomes for study participants with an intercurrent event are treated as though they had completed the randomized study treatment through Week 16 by imputing data following an intercurrent event using multiple imputation (MI).
4. Study participant-level summary measure: Difference in the adjusted means between bimekizumab and placebo.

Any missing data not associated with discontinuation of IMP will also be imputed using MI.

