9.4 Planned safety and other analyses

Safety variables will be analyzed for all study participants in the SS.

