9.4.1.6 PHQ-9

Change from Baseline in PHQ-9 score will be summarized over time by treatment group. The number of study participants with a PHQ-9 score ≥ 15 and ≥ 20 at any time will be summarized.

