9.6 Handling of dropouts or missing data

Pharmacokinetic analyses will be based on observed data; no imputation will be used. However, if plasma concentration measurements are below the level of quantification, then for calculation of the derived statistics the result will be set to half of the lower level of quantification.

Study participants who prematurely discontinue IMP (intercurrent event) will have their data imputed under the estimand framework described in Section 9.3.1.

Missing data outside of an intercurrent event for the binary (responder) efficacy variables will be imputed; study participants with missing data will be considered as nonresponders for the respective time point. Missing data for the continuous secondary efficacy variable percentage change from Baseline in BSA affected by PSO will be imputed using MI. If the imputation model cannot converge, the LOCF method will be used. Further details will be provided in the SAP.

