5.1.1.7 Handling of dropouts or missing data

Details about approaches to handle missing data are described in this section.

Efficacy missing data 5.1.1.7.4

An intercurrent event is defined as discontinuation of IMP prior to Week 16.

For study participants who experience an intercurrent event, the intercurrent event date is defined as:

Last study treatment date + 28 days (dosing interval) + 3 days (visit window)

For both co-primary endpoints (PASI90 and IGA 0/1 at Week 16), participants with an intercurrent event will be considered as nonresponder.

For secondary efficacy binary endpoints (PASI100 response at Week 16, IGA 0 response at Week 16, PSD [P-SIM] [itch, pain, and scaling] response at Week 16, Scalp IGA 0/1 response at Week 16, and DLQI 0/1 response at Week 16), study participants with intercurrent event will be handled using the same approach as the co-primary endpoints.

For PASI75 response at Week 4, a study participant will be considered a nonresponder only if the intercurrent event date occurs prior to the date of the Week 4 assessment.

Any missing data for the primary and secondary binary endpoints not associated with discontinuation of IMP will also be imputed as a nonresponse.

For the secondary continuous endpoint (percent change from baseline in BSA affected by PSO), participants with an intercurrent event are treated as though they had completed the randomized study treatment through Week 16 by imputing data following an intercurrent event using LOCF (see section 5.4.1.2.2). In addition, missing data not associated with discontinuation of IMP will also be imputed using LOCF.

For all tertiary endpoints, all data collected after an intercurrent event will be treated as missing and subject to imputation as described in section 5.5.

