#### Patient Health Questionnaire 9 (PHQ-9) scores 5.6.3.6

The PHQ-9 is a multipurpose instrument for screening, diagnosing, monitoring, and measuring the severity of depression. The PHQ-9 scores for depression range from 0 to 27 with higher scores indicating worse state. A score of 5-9 is considered to be minimal symptoms of depression. A score of 10 to 14 is considered minor depression, dysthymia, or mild major depression. A score of 15 to 19 is considered to indicate moderately severe major depression, and a score  $\geq 20$  is considered to be severe major depression.

Change from Baseline in PHQ-9 is derived as post-Baseline score minus Baseline score and will be summarized by treatment group.

PHQ-9 is a Safety parameter described on the Safety Population by actual treatment group. Nevertheless, identification of observable data and implementation of LOCF imputation is done the same way as Efficacy parameters.

A Table presenting the number of study participants with PHQ-9 total score  $\geq 15$  and  $\geq 20$  at all scheduled visits (including Screening, Baseline and each visit through the Treatment Period) and overall at any post-baseline visit will be provided by treatment group using observed case data.

A by-study participant listing of the PHQ-9 questionnaire data will be provided by treatment group including the increase of PHQ-9 scores from the previous visit.

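### SAP Appendix 2 presents LOCF for PHQ-9 as replacing a multiple imputation that the protocol never specified, and SAP 5.6.3.6 can be read as replacing scores measured after treatment stops

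*SAP*

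**What the plan says.** **Protocol.** Section 3 lists "Change from Baseline in PHQ-9 at Week 16" as a secondary endpoint, under an objective about whether depression appears or gets worse. Section 9.4 sets the population: "Safety variables will be analyzed for all study participants in the SS". Section 9.4.1.6 gives the analysis: "Change from Baseline in PHQ-9 score will be summarized over time by treatment group", plus counts of scores at or above 15 and 20. It names no method for missing PHQ-9 scores. On MI, Section 9.6 states: "Missing data for the continuous secondary efficacy variable percentage change from Baseline in BSA affected by PSO will be imputed using MI".

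**SAP.** Appendix 2 (6.2) records that MI for BSA is replaced by LOCF because the study is small. It extends the same update to PHQ-9, "of which the missing data will be imputed using LOCF instead of MI approach". Section 5.6.3.6 calls PHQ-9 a safety parameter but adds that "identification of observable data and implementation of LOCF imputation is done" in the same manner as for efficacy parameters. For BSA, Section 5.1.1.7 treats participants who stop early as if they had completed "study treatment through Week 16 by imputing data following an intercurrent event using LOCF". The intercurrent event date is the last dose plus 28 days plus 3 days.

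**The concern.** Two things look wrong.

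First, Appendix 2 exists to record departures from the protocol, and here it misdescribes one. A reader would conclude that PHQ-9 imputation was always planned and that only the technique changed.

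Second, the efficacy rule answers a hypothetical question: what would have been seen had the participant stayed on treatment. For a depression safety endpoint the interest is in what was actually recorded. Stopping is also not independent of the outcome, since PHQ-9 results are among the withdrawal criteria in Protocol 7.1. If the efficacy rule decides which PHQ-9 scores count, a real score taken after stopping could give way to an earlier one in the Week 16 mean change.

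**Working it through.** The plan gives no figure for PHQ-9 to reproduce, and the 95% power for PASI90 does not bear on this point. The check is mainly a comparison of texts.

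**1. Did the protocol specify MI for PHQ-9?** MI appears in three places:
- Section 9.3.1, within the BSA estimand, including the closing line "Any missing data not associated with discontinuation of IMP will also be imputed using MI";
- Section 9.3.3, for the BSA ANCOVA, with LOCF as a fallback;
- Section 9.6, which names BSA.

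Section 9.6 also sends the data of participants who stop IMP to the framework in 9.3.1, but 9.3.1 covers efficacy endpoints only. So no MI was specified for PHQ-9, and the protocol is silent on its missing scores.

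**2. Which rule does SAP 5.6.3.6 import?** It borrows the efficacy approach for two steps: deciding which data are observable, and applying LOCF. The only efficacy endpoint with LOCF is BSA (SAP 5.1.1.7 and 5.4.1.2.2), where data after the intercurrent event date are imputed. No exemption for PHQ-9 is stated.

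**3. Which scores are exposed?** Counting days after the first dose, with dosing on schedule:
- Last dose at Week 8: 8 × 7 = 56, and 56 + 28 + 3 = 87. The Week 12 window is 84 ± 3, ending on day 87.
- Last dose at Week 12: 12 × 7 = 84, and 84 + 28 + 3 = 115. The Week 16 window is 112 ± 3, ending on day 115.

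A PEOT held within the next visit's window is therefore kept. After PEOT the only planned visit is Safety Follow-Up, whose PHQ-9 data are only listed (SAP 5.1.1.1.3). What remains is a late PEOT, or a PEOT after a missed dose.

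**4. Does a conflict arise?** Suppose the last dose is at Week 8, Week 12 is attended without dosing, and PEOT falls on day 98. SAP 5.1.1.1.4 assigns that PEOT to Week 16 and says that a mapped visit is summarized as observed. But 98 > 87, so the BSA rule would instead carry forward the Week 12 score. The two sections give different Week 16 values for one participant.

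**5. How much could it move the mean?** Assume one participant's measured score differs by d points from the carried-forward one. The arm mean shifts by d/n, with the planned arm sizes (30 and 15):

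| d (assumed) | n = 30 | n = 15 |
|---|---|---|
| 5 | 0.17 | 0.33 |
| 10 | 0.33 | 0.67 |
| 15 | 0.50 | 1.00 |
| 20 | 0.67 | 1.33 |

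**The case against.** The strongest reply is that no sentence orders a measured PHQ-9 score to be discarded. Appendix 2 speaks only of missing PHQ-9 data, whereas for BSA it separately names outcomes after an intercurrent event. The post-event LOCF rule in SAP 5.1.1.7 names only BSA, and SAP 5.5.2 gives tertiary continuous efficacy variables no imputation, so likeness to efficacy parameters is ambiguous. This stands: replacement is an inference. It does not remove the problem, because SAP 5.1.1.7 also treats post-event data for tertiary endpoints as missing. On that reading a measured PHQ-9 score would be set aside rather than replaced.

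A reader might infer that the protocol ruled out imputing PHQ-9. It did not. Section 9.4.1.6 is silent, whereas Section 9.3.4 states expressly that tertiary continuous efficacy variables are not imputed.

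A reader might also infer that LOCF hides worsening and must go. The documents do not support that either. A participant withdrawn after a high score would have that score carried into the Week 16 mean by LOCF, while an observed-case summary would drop the participant. Either method can mislead, in either direction.

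Finally, exposure is narrow. The threshold table in SAP 5.6.3.6 uses observed cases, the listing shows the questionnaire data, and no formal test depends on PHQ-9. All of this stands and limits the weight of the point.

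**Conclusion.** The point holds in a limited form. It is certain from the text that Appendix 2 misdescribes the protocol: MI was specified for BSA alone, so LOCF for PHQ-9 is new. It is a fair inference, not an explicit statement, that SAP 5.6.3.6 read with the BSA rule would replace a PHQ-9 score measured more than 31 days after the last dose, in conflict with SAP 5.1.1.1.4.

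The effect is probably small. It is confined to the change-from-Baseline summary and to late PEOT visits or those after a missed dose, and its direction is unknown. The shifts of 0.17 to 1.33 points assume a single affected participant, a difference of 5 to 20 points, and full planned arms. The point still merits correction because the endpoint is a secondary safety endpoint, the arms are small, and the remedy costs almost nothing.

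**What to change.** - **SAP 5.6.3.6:** state that every PHQ-9 score measured in the Treatment Period, including after IMP is stopped, is used as observed and is not replaced under the efficacy intercurrent-event rule. Define observed here explicitly, because the observed-case analyses in SAP 5.4.1.3 set participants who stopped IMP to missing.
- **Presentation:** give change from Baseline on observed values in the Safety Set. If a LOCF version is kept, show it alongside, apply it only to scores that are truly missing, and label it as an addition to the protocol.
- **Appendix 2:** say that the protocol specified no MI for PHQ-9 and that LOCF for it is new.

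The cost is SAP wording and, if both versions are shown, one extra summary. The observed Week 16 mean will include fewer participants; the LOCF version beside it offsets that loss.
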